The time period for safety analysis of the 24-week interim analysis will be following criteria whichever occurs first:

- up to last dose plus up to 30 days in the study
- the first dose in Period 3
- up to dose change or up to the data cutoff date

The time period for safety analysis of the 52-week interim analysis will be following criteria whichever occurs first:

- up to last dose plus up to 30 days in the study
- the study discontinuation date
- up to dose change
- the first dose date in Period 3

**The time period for safety analysis of the 104 interim analysis** will be following criteria whichever occurs first:

- up to last dose plus up to 30 days in the study
- the study discontinuation date
- up to dose change date due to rescue

- up to dose change date due to retreatment
- the first dose in Period 4
- up to the data cutoff date

**The time period for safety analysis of the final analysis** will be following criteria whichever occurs first:

- up to last dose plus 30 days or up to last date in the study
- the study discontinuation date
- up to dose change

**Long-Term Extension (LTE) Substudy Population:** The LTE Substudy Population is defined as the patients who received at least one study medication in Period 3 of Study JAIN, and entered the downtitration substudy. Additionally, those patients who did not met study discontinuation criteria in Period 3 and continued in Period 4 will be considered in the analysis set.

**Long-Term Extension(LTE) Substudy Relapse Population:** for a subset of patients in the LTE Substudy Population defined as above who experienced a relapse in Period 3 or Period 4 (IGA $\geq$ 3 after Week 52).

**Long-Term Extension(LTE) Non-responder Population:** The LTE Non-responder Population is defined as the patients who received at least one study medication in Period 3 of Study JAIN, and IGA $\geq$ 3 at Week 52. Additionally, those patients who did not met study discontinuation criteria in Period 3 and continued in Period 4 will be considered in the analysis set.

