Postbaseline visits for weekly assessments of daily diary data will be each 7-day visit interval beginning on the day of first study drug administration, creating intervals for Week 1 (Days 1 through 7), Week 2 (Days 8 through 14), Week 3 (Days 15 through 21),..., Week 50 (Day 344 through 350). Each interval will be represented by the mean of that interval. If there are less than 4 non-missing measurements in any weekly interval, the mean for that weekly visit interval will be considered missing. Furthermore, as some analyses require use of the primary censoring rule (Section 6.3), assessments collected on or after the day of rescue will be excluded from the weekly visit interval calculation when implementing this censoring rule. If, after exclusion of those records, there are less than 4 non-missing assessments, the mean of the weekly interval that implements the primary censoring rule will be considered missing.

Week 52 diary window is the 7 days prior to Week 52 (V14) visit date. If Week 52 (V14) visit occurs later than Days 370 (=365+5), the window is from Days 358 through 364. If there is no Week 52 (V14) visit, the Week 52 interval and its associated mean are defined as missing. Week 51 diary window is from Days 351 through 357, but will exclude the dates falling into Week 52 diary window.

Week 53 diary window is from Days 365 through 371, but will exclude the dates falling into Week 52 diary window. Week 54 is from Days 372 through 378; Week 55 is from Days 379 through 385. Week 68 is from Days 470 through 476. If there are less than 4 non-missing measurements in any weekly interval, the mean for that weekly visit interval will be considered missing.

For the Week-104 interim lock, safety analyses will be conducted for adverse events (AE) for Treatment Period 3. The AE baseline period is on/after the first dose date in Period 2 and prior to the date of the first dose date in Period 3 of Study JAIN.

For the Final lock, safety analyses will be conducted for adverse events (AE) on extended safety analysis for which baseline will be Week 0 i.e. on/after the first dose date in Period 2Postbaseline measures for the safety analyses are defined as the non-missing scheduled (planned) measurements after the date of first study drug administration for continuous measures, by-visit analyses, and all non-missing measurements after the date of first study drug administration for all other analyses.

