## 6.13. Safety Analyses

The general methods used to summarize safety data, including the definition of baseline value are described in Section 6.2.2.

Safety analyses will include all data including rescue to any of the 3 rescue therapy options, unless otherwise stated, and patients will be analyzed according to the investigational product to which they were randomized at Week 0 (Visit 2). For 24-week and 52-week interim lock, safety analyses will use the safety population defined in Section 6.2.1.

For the 24-week and 52-week interim lock, safety topics that will be addressed include the following: AEs, clinical laboratory evaluations, vital signs and physical characteristics, Columbia Suicide Severity Rating Scale (C-SSRS), the Self-Harm Supplement Form, safety in special groups and circumstances, including adverse events of special interest (AESI) (see Section 6.13.4), and investigational product interruptions.

Unless otherwise specified, by-visit summaries will include planned on-treatment visits. For tables that summarize events (such as AEs, categorical laboratory abnormalities, shift to maximum severity), post-last dose follow-up data will be included. Follow-up data is defined as all data occurring up to 30 days (planned maximum follow-up time) after last dose of treatment including rescue, regardless of study period. All safety data from continuing patients at time of the 52-week interim lock will be included in the safety analysis up to the first dose date of period 3. Safety data from patients who permanently discontinued study drug prior to an interim lock will be included in the interim lock safety analysis up to 30 days post last dose.

For the 104-week interim analysis safety topics will be addressed including the following: AEs and AESI (i.e., infections, MACE, VTE, Malignancies).

For the final analyses, safety analyses will use the safety population and Extended Safety analysis will be performed by treatment based on the initial randomization at week 0 including the All BARI group, who received at least one dose of BARI during the study, to address both the safety topics including AEs and AESI (i.e., infections, MACE, VTE, Malignancies). The Compound level safety standards provide further details and information.

Duration of exposure (in days) will be calculated as follows:

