- Duration of exposure to investigational product (including exposure after the initiation of rescue therapy): *date of last dose of study drug including rescue – date of first dose of study drug + 1*

Duration of exposure (in days) for the “PBO/BARI 1-mg to BARI 2-mg” and the “PBO/BARI 1-mg/BARI 2-mg to BARI 4-mg” groups will be calculated as follows:

- Duration of exposure to investigational product (including exposure after the initiation of rescue therapy): *date of last dose of study drug including rescue – date of first dose of study drug after the switch + 1*

Last dose of study drug including rescue is calculated as last date on study drug. See the Compound level safety standards for more details.

Total patient-years (PY) of exposure will be reported for each treatment group for overall duration of exposure. Descriptive statistics will be provided for patient-days of exposure, and the frequency of patients falling into different exposure ranges in addition to cumulative exposures will be summarized.

Exposure ranges will be reported in weeks using the following:

- ≥4 weeks, ≥8 weeks, ≥12 weeks, ≥16 weeks, ≥24 weeks, ≥52 weeks, ≥76 weeks, ≥104 weeks, ≥120 weeks, ≥136 weeks, ≥152 weeks, ≥168 weeks, ≥184 weeks and ≥200 Weeks
- >0 to <4 weeks, ≥4 weeks to <8 weeks, ≥8 weeks to <12 weeks, ≥12 to <16 weeks, ≥16 to 24 weeks, ≥24 to 52 weeks, ≥52 to 76 weeks, ≥76 to 104 weeks, and ≥104 to 120 weeks, ≥120 to 136 weeks, ≥136 to 152 weeks, ≥152 to 168 weeks, ≥168 to 184 weeks, ≥184 to 200 weeks, ≥200 Weeks

The exposure ranges for the interim lock(s) will be adjusted accordingly.

**For Week-104 interim analysis**, exposure ranges will be reported in weeks using the following:

- ≥52 weeks, ≥60 weeks, ≥68 weeks, ≥76 weeks, ≥92 weeks, and ≥104 weeks
- ≥52 weeks to <60 weeks, ≥60 weeks to <68 weeks, ≥68 to <76 weeks, ≥76 to 92 weeks, ≥92 to 104 weeks, and ≥104 weeks

**For final analysis**, exposure ranges will be reported in weeks using the following:

- ≥52 weeks, ≥60 weeks, ≥68 weeks, ≥76 weeks, ≥92 weeks, ≥104 weeks, ≥120 weeks, ≥136 weeks, ≥152 weeks, ≥168 weeks, ≥184 weeks, ≥200 weeks
- ≥52 weeks to <60 weeks, ≥60 weeks to <68 weeks, ≥68 to <76 weeks, ≥76 to 92 weeks, ≥92 to 104 weeks, and ≥104 to 120 weeks, ≥120 to 136 weeks, ≥136 to 152 weeks, ≥152 to 168 weeks, ≥168 to 184 weeks, ≥184 to 200 weeks, ≥200 Weeks

Overall exposure will be summarized in total PY, which is calculated according to the following formula:

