For selected safety topics, incidence rate (IR) per 100 patient-years of observation (PYR) will be provided for the Week 52, Week 104, and final analyses. See the Compound level safety standards for more details.

Adverse Events and Treatment Emergent AEs will be replicated based on the Safety Censoring rule 1 and 2.

Safety censoring rule 1 excludes the event if it's after the permanent study drug discontinuation, or dose change, whichever occurred earlier and Safety censoring rule 2 excludes the event if it's after the permanent study drug discontinuation.

Extended Safety Analysis includes patients who were continuously treated with Baricitinib 1mg, 2mg, or 4mg and Placebo from baseline and censored in case of dose change using Safety Censoring Rule 1. In addition to the above treatment groups “ALL BARI” will also be included to the summary which includes patients who received at least one dose (1 mg, 2mg, or 4mg) of BARICITINIB at any time of the treatment period.

In an overview table, the number and percentage of patients in the safety population who experienced death, an SAE, any TEAE, discontinuation from the study due to an AE, permanent

discontinuation from study drug due to an AE, TEAEs which are considered related to treatment by the investigator, or a severe TEAE will be summarized by treatment group.

The number and percentage of patients with TEAEs will be summarized by treatment group in 2 formats:

- by MedDRA PT nested within SOC with decreasing frequency in SOC, and events ordered within each SOC by decreasing frequency in the All baricitinib group
- by MedDRA PT with events ordered by decreasing frequency in the All baricitinib group.

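### At the final lock the SAP's safety window, its Censoring Rule 2 and its All Bari group disagree on whether, and where, events after a dose change count

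*SAP*

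**What the plan says.** Dose changes are part of the design from Week 52. Under Protocol 5.1.3.2, placebo, 1-mg and 2-mg patients outside the substudy with IGA of 3 or more are rerandomised 1:1 to 2-mg or 4-mg. Under Protocol 5.1.3.1, half of the substudy patients step down from 4-mg to 2-mg or from 2-mg to 1-mg, and return to the earlier dose on relapse.

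Five statements in the SAP then govern safety at the final lock.

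- **6.2.1, window.** The list introduced by "The time period for safety analysis of the final analysis" takes the earliest of three stops, and the last of these is dose change. No group is exempted.
- **6.13.1, dose columns.** The Extended Safety Analysis covers "patients who were continuously treated with Baricitinib 1mg, 2mg, or 4mg and Placebo from baseline and censored in case of dose change", using Rule 1. The Safety Population row of Table JAIN.6.3 says much the same, and lists All Bari among its groups without describing it separately.
- **6.13.1, two rules.** "Adverse Events and Treatment Emergent AEs will be replicated based on the Safety Censoring rule 1 and 2". Rule 1 drops an event that falls "after the permanent study drug discontinuation, or dose change, whichever occurred earlier and Safety censoring rule 2 excludes the event" only when it follows permanent discontinuation. Rule 2 therefore keeps events after a dose change.
- **6.13.1, All Bari.** This group takes in "patients who received at least one dose (1 mg, 2mg, or 4mg) of BARICITINIB at any time of the treatment period".
- **6.13 and 6.2.2.1, arm and start.** "Extended Safety analysis will be performed by treatment based on the initial randomization at week 0", with All Bari added. The start is the "extended safety analysis for which baseline will be Week 0". Section 6.13.1 likewise counts an event as treatment-emergent from the first dose of study treatment, which for a placebo patient is placebo.

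**The concern.** A placebo patient can enter All Bari only by changing treatment, yet the 6.2.1 window closes at that moment. The group's definition and the window therefore cannot both hold. Dropping the window leaves a second problem: nothing moves such a patient's start from Week 0 to the first baricitinib dose, so a year of placebo experience can enter a baricitinib column.

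Rule 2 raises a related question. The SAP does not say which columns the Rule 2 run fills, and the only grouping rule given for the final analysis is the Week 0 arm.

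At stake is the long-term safety reporting, which Protocol 5.4 gives as one purpose of the bridging extension. All Bari would be either truncated or mixed with placebo time. No hypothesis test is affected, because SAP 6.2.2.3 makes Period 3 and 4 safety descriptive.

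**Working it through.** The SAP gives no figure to reproduce, so the check traces two patients through the stated rules.

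**Patient 1:** randomised to placebo, IGA of 3 or more at Week 52, rerandomised to 4-mg. Event A occurs on placebo before the switch and event B on 4-mg after it.

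**Patient 2:** randomised to 2-mg, stepped down to 1-mg in the substudy. Event C occurs on 1-mg.

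| Rule applied as written | A | B | C |
|---|---|---|---|
| 6.2.1 window, all groups | Placebo; also All Bari if the start is Week 0 | Not counted | Not counted |
| Rule 1, dose and placebo columns | Placebo | In no dose column | In no dose column |
| Rule 2, by Week 0 arm (6.13) | Placebo | Placebo | 2-mg |
| All Bari, no dose-change cut, Week 0 start | All Bari | All Bari | All Bari |

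Row 1 leaves Patient 1 in the All Bari N with no baricitinib follow-up. If the Week 0 start also applies, the only time left for that patient is placebo time. Event C is lost from All Bari even though Patient 2 never left baricitinib. Row 3 puts an event on 4-mg under placebo. Row 4 puts an event on placebo under baricitinib. Only row 2 does what its label says.

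**Scale, for illustration.** Arm sizes of 100 placebo, 100 1-mg, 200 2-mg and 100 4-mg come from Protocol 5.1. The other inputs are assumed: Week 52 completion c = 0.70-0.85; nonresponse (IGA of 3 or more) among placebo, 1-mg and 2-mg completers n = 0.40-0.60; nonresponse on 4-mg m = n or n - 0.10; and every IGA 0-2 patient on 2-mg or 4-mg enters the substudy. Later relapses are not counted.

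- Placebo patients switched at Week 52 = 100cn. Low: 100 x 0.70 x 0.40 = 28. High: 100 x 0.85 x 0.60 = 51.
- All Bari N = 400 + 100cn = 428 to 451. Switched placebo share: 28/428 = 6.5% to 51/451 = 11.3%.
- Placebo time at risk of entering All Bari: about one year each (52 x 7 / 365.25 = 0.997), so roughly 28-51 patient-years.
- Share of Week 52 completers who change dose at Week 52 = [300n + 100(1 - n) + 50(1 - m)]/500. Low (n = m = 0.40): (120 + 60 + 30)/500 = 42%. High (n = 0.60, m = 0.50): (180 + 40 + 25)/500 = 49%. Completion cancels.
- With 70% substudy entry the share is 37-45%. With n from 0.20 to 0.70 and full entry it is 36-52%.

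The last two lines show how much follow-up the 6.2.1 cut could touch if it applied to All Bari.

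**The case against.** There is a coherent reading, and it is probably the intended one. The 6.2.1 window is simply Rule 1. Section 6.13.1 ties Rule 1 to the dose and placebo columns and then adds All Bari, which Rule 2 supplies. A default window with a named replicate is not in itself a contradiction. That 6.2.1 would leave switched placebo patients with no baricitinib time suggests it was never meant to govern All Bari.

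Much of this stands, but no sentence says it: 6.2.1 states no exception and 6.13.1 does not assign Rule 2 to a column. Nor does this reading settle where All Bari starts.

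Two stronger conclusions might be inferred, and the documents support neither.

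- *That the plan fails to report safety by the dose taken after a switch.* The SAP names no such event table at the final lock. However, 6.13 computes exposure from the first dose after the switch for two groups, one labelled "PBO/BARI 1-mg/BARI 2-mg to BARI 4-mg", and it refers to the Compound level safety standards there, at the Extended Safety sentence, and for incidence rates in 6.13.1. Those standards were not supplied and may specify the tables. The 104-week lock also has its own Period 3 AE baseline, and its window ends at rescue or retreatment rather than at any dose change, so it covers part of Period 3. SAEs, deaths and adjudicated events are listed individually as well.
- *That the plan directs baricitinib events into the placebo column.* Table JAIN.6.3 and the Extended Safety text both censor that column at dose change. The misplacement arises only if Rule 2 is tabulated by Week 0 arm. That follows from combining 6.13 with 6.13.1, but no display instructs it.

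**Conclusion.** The concern holds as a conflict between stated rules at the final lock. Applied literally, 6.2.1 empties All Bari of follow-up after a dose change. Set aside, it leaves a Week 0 start that admits placebo-period events of switched placebo patients. The columns for Rule 2 are not defined. Censoring at dose change is a sound way to keep the dose columns clean and should stay.

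This is a minor point, worth correcting because the correction is cheap. Confidence is medium, since the unseen standards may resolve some of it in practice. The figures of 28-51 switched placebo patients and 42-49% of completers changing dose indicate scale only: nonresponse and retention are not in the documents. Applying the 42-49% to later patient-time would also need equal dropout across groups. Protocol 5.1.3.2 makes that doubtful, because it advises considering discontinuation when symptoms stay unacceptable after IGA reaches 3. If Week 52 nonresponders contributed half the later time of the others, the range would fall to about 38-44%.

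**What to change.** Three wording changes:

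1. In SAP 6.2.1, limit the dose-change stop in the final-analysis window to the Rule 1 dose and placebo columns.
2. In SAP 6.13.1 and the Safety Population row of Table JAIN.6.3, state that All Bari counts events and time from the first baricitinib dose to permanent discontinuation plus up to 30 days, across dose changes.
3. In SAP 6.13.1, state which columns the Rule 2 run fills. If they are by Week 0 arm, label them as including events on a later dose.

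Optional, and not the correction of an error: tie descriptive event summaries to the post-switch groups already named for exposure in SAP 6.13, or cite the section of the Compound level safety standards that does so. Label them as selected patients without a concurrent randomised placebo group.

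The cost is a few sentences in the SAP and some relabelled descriptive tables.

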#### **6.13.1.1. Common Adverse Events**

Common TEAEs are defined as TEAEs that occurred in  $\geq 2\%$  (before rounding) of patients in any treatment group including placebo. The number and percentage of patients with common TEAEs will be summarized by treatment using MedDRA PT ordered by decreasing frequency in the All baricitinib group.

The number and percentage of patients with TEAEs will be summarized by maximum severity by treatment using MedDRA PT ordered by decreasing frequency in the All baricitinib group for the common TEAEs. For each patient and TEAE, the maximum severity for the MedDRA level being displayed is the maximum postbaseline severity observed from all associated LLTs mapping to that MedDRA PT.

#### **6.13.1.2. Serious Adverse Event Analyses**

Consistent with the International Conference on Harmonisation (ICH) E2A guideline (1994) and 21 Code of Federal Regulations (CFR) 312.32 (a) (2010), an SAE is any AE that results in any one of the following outcomes:

- Death
- Initial or prolonged inpatient hospitalization
- A life-threatening experience (that is, immediate risk of dying)
- Persistent or significant disability/incapacity
- Congenital anomaly/birth defect

Important medical events that may not be immediately life-threatening or result in death or hospitalization but may jeopardize the patient or may require intervention to prevent one of the other outcomes listed in the definition above should be considered as serious. See examples in the ICH E2A guideline Section 3B.

The number and percentage of patients who experienced any SAE will be summarized by treatment using MedDRA PT nested within SOC. Events will be ordered by decreasing frequency in the All baricitinib group within decreasing frequency in SOC. The SAEs will also be summarized by treatment using MedDRA PT without SOC.

An individual listing of all SAEs will be provided. A listing of deaths, regardless of when they occurred during the study, will also be provided.

### 6.13.1.3. Other Significant Adverse Events

Other significant AEs to be summarized will provide the number and percentage of patients who

- permanently discontinued study drug because of an AE or death, and
- temporarily interrupted study drug because of AE

by treatment using MedDRA PT nested within SOC. Events will be ordered by decreasing frequency in the All baricitinib group within decreasing frequency in SOC.

A summary of temporary interruptions of study drug will also be provided, showing the number of patients who experienced at least 1 temporary interruption and the number of temporary interruptions per patient with an interruption. Further, the duration of each temporary interruption (in days), the cumulative duration of dose interruption (in days) using basic descriptive statistics, and the reason for dose interruption will be provided.

A listing of all AEs leading to permanent discontinuation from the study drug or from the study will be provided. A listing of all temporary study drug interruptions, including interruptions for reasons other than AEs, will be provided.

### 6.13.1.4. Criteria for Notable Patients

Patient narratives will be provided for all patients who experience certain “notable” events prior to data cutoff date for the submission. See the Compound level safety standards for a list of criteria.

## 6.13.2. Clinical Laboratory Evaluation

For the categorical laboratory analyses (shift and treatment-emergent), the analysis period is defined as the treatment period plus up to 30 days off-drug follow-up time. The analysis period for the continuous laboratory analyses (for example, change from baseline by time point) is defined as the treatment period excluding off-drug follow-up time.

All laboratory tests will be presented using the International Système (SI) and US conventional (CN) units. The performing central laboratory reference ranges will be used to define the low and high limits. Key results pertaining to the 4 key hepatic laboratory assessments (alanine aminotransferase [ALT], aspartate aminotransferase [AST], total bilirubin, and alkaline phosphatase [ALP]) will be included as a separate analysis to address the risk of liver injury as a special safety topic (see Section 6.13.4.1).

There is 1 special circumstance for laboratory values to be derived based on regularly scheduled, protocol-specified analytes. The low-density lipoprotein/high-density lipoprotein (LDL/HDL) ratio will be derived as the ratio of LDL cholesterol to HDL cholesterol. There are no central lab reference ranges for the LDL/HDL ratio.

The following will be conducted for the laboratory analytes collected quantitatively:

- **Box plots:** Values at each visit (starting from randomization) and change from last baseline to each visit and to last postbaseline measure will be displayed in box plots for patients who have both a baseline and at least 1 postbaseline visit. The last non-missing observation in the treatment period will be used as the last observation. Individual measurements outside of reference limits will also be displayed using distinct symbols overlaying the box plot. Original-scale data will be used for the display but for some analytes (for example, immunoglobulins) a logarithmic scale may be used to aid in viewing the measures of central tendency and dispersion. Unplanned measurements will be excluded. Descriptive summary statistics will be included below the box plot along with p-values resulting from between treatment comparison in change from last baseline to last observation. An ANCOVA model with explanatory term for treatment and the baseline value as a covariate will be used. These box plots will be used to evaluate trends over time and to assess a potential impact of outliers on central tendency summaries.
- **Treatment-emergent high/low analyses:** The number and percentage of patients with treatment-emergent high and low laboratory results at any time will be summarized by treatment group. Planned and unplanned measurements will be included. A treatment-emergent **high** result is defined as a change from a value less than or equal to the high limit at all baseline visits to a value greater than the high limit at any time during the treatment period. A treatment-emergent **low** result is defined as a change from a value greater than or equal to the low limit at all baseline visits to a value less than the low limit at any time during the treatment period. The Fisher's exact test will be used for the treatment comparisons.

For laboratory analyte measurements collected qualitatively, a listing of abnormal findings will be provided. The listing will include but not be limited to patient identifier (ID), treatment group, laboratory collection date, analyte name, and analyte finding. If needed by the safety physician/scientist, for analytes measured qualitatively, the number and percentage of patients with treatment-emergent abnormal laboratory results at any time will be summarized by treatment. Planned and unplanned measurements will be included. A treatment-emergent abnormal result is defined as a change from normal at all baseline visits to abnormal at any time postbaseline.

The listing of specific reference ranges used in analysis of laboratory data will be provided.

Note that additional analyses of certain laboratory analytes will be discussed within subsections of Section 6.13.4 pertaining to Special Safety topics (Section 6.13.4.1 for hepatic analytes, Section 6.13.4.2 for analytes related to hematologic changes, Section 6.13.4.3 for analytes related to lipids, Section 6.13.4.4 for analytes related to renal function, and Section 6.13.4.5 for creatine phosphokinase [CPK]).

